4.1.3 Handling and Dispensing

The product storage manager should ensure that the study drug is stored in accordance with the environmental conditions (temperature, light, and humidity) as determined by BMS. If concerns regarding the quality or appearance of the study drug arise, the study drug should not be dispensed and contact BMS immediately.

Investigational product documentation must be maintained that includes all processes required to ensure drug is accurately administered. This includes documentation of drug storage, administration and, as applicable, storage temperatures, reconstitution, and use of required processes (eg, required diluents, administration sets). Refer to the BMS-936558 (nivolumab) investigator brochure or ipilimumab package insert for details related to handling and dose preparation, as well as any pharmacy instruction sheets.

For non-investigational product, if marketed product is utilized, it should be stored in accordance with the package insert, summary of product characteristics (SmPC), or similar.

4.2 Method of Assigning Subject Identification

The subject number will be assigned through an interactive voice response system (IVRS) once the subject has signed the informed consent form and is registered. Every subject that signs the informed consent form must be assigned a subject number in IVRS. Specific instructions for using IVRS will be provided to the investigational site in a separate document.

The investigator or designee will register the subject for enrollment by following the enrollment procedures established by BMS. The following information is required for enrollment:

- Date that informed consent was obtained
- Date of birth
- Gender at birth

Once enrolled in IVRS, enrolled subjects that have signed the informed consent form and met all eligibility criteria will be randomized through the IVRS. The following information is required for subject randomization:

- Subject number
- Date of birth
- Gender at birth
- Date of informed consent

Subjects meeting all eligibility criteria will be randomized in a 1:1 ratio to Cohort A (nivolumab followed by ipilimumab) or Cohort B (ipilimumab followed by nivolumab).

4.3 Selection and Timing of Dose for Each Subject

Dosing calculations should be based on the body weight assessed at each visit as per Table 5.1-2, Table 5.1-3, and Table 5.1-4. All doses should be rounded to the nearest milligram. There will be no nivolumab or ipilimumab dose escalations or reductions permitted.

The first dose of study drug will be administered on Week 1, Day 1. Subsequent doses are to be scheduled from the calendar date of the first dose and have a +/- 3 day dosing window. Please refer to Table 5.1-2 and Table 5.1-3 for the appropriate timing of doses (in terms of number of Weeks/Days from first dose) in the Induction Period.

After each nivolumab dose, the next dose of study treatment may be given no sooner than 12 days later. After each ipilimumab dose, the next dose of study treatment may be given no sooner than 19 days later.

There are no premedications recommended for nivolumab or ipilimumab. Subjects should be carefully monitored for infusion reactions during nivolumab and ipilimumab administration. If an infusion reaction is noted, subjects should be managed according to Section 4.3.4.3.

There will be no dose delays permitted in this study. Doses of nivolumab or ipilimumab will be omitted if omission criteria, described in Section 4.3.4.1, are met. Treatment may resume at the next scheduled dose if retreatment criteria (specified in Section 4.3.4.2) are met.

The maximum duration of study treatment to be administered to an invididual subject is 2 years from the first study treatment in Induction Period 1.

4.3.1 Induction Period 1

Induction Period 1 will be the first 12 weeks of study treatment (Weeks 1 to 13).

• Subjects in Cohort A will receive nivolumab at a dose of 3 mg/kg as a 60 minute IV infusion every 2 weeks (14 days) for up to 6 doses.

• Subjects in Cohort B will receive ipilimumab at a dose of 3 mg/kg as a 90 minute IV infusion every 3 weeks (21 days) for up to 4 doses.

4.3.2 Induction Period 2

After completion of Induction Period 1, subjects will proceed to Induction Period 2 (12 weeks duration, from Week 13 to 25), regardless of the results of the tumor assessment at the end of Induction Period 1.

- Subjects in Cohort A will receive ipilimumab at a dose of 3 mg/kg as a 90 minute IV infusion every 3 weeks (21 days) for up to 4 doses.
- Subjects in Cohort B will receive nivolumab at a dose of 3 mg/kg as a 60 minute IV infusion every 2 weeks (14 days) for up to 6 doses.

4.3.3 Continuation Period

• Subjects in both Cohorts A and B will receive nivolumab at a dose of 3 mg/kg as a 60 minute IV infusion every 2 weeks (14 days), starting at Week 25 until disease progression, unacceptable toxicity, or withdrawal of consent, for a maximum duration of up to 2 years from the first study treatment in Induction Period 1.

4.3.4 Dose Modifications for Nivolumab and Ipilimumab

Subjects will be monitored continuously for AEs while on study. Treatment modifications (eg, dose omissions) will be based on specific laboratory and AE criteria.

In some cases, the natural history of AEs associated with immunotherapy can differ and be more severe than AEs caused by other therapeutic classes. Early recognition and management may mitigate severe toxicity. The following Recommended Management Algorithms for nivolumab were developed to assist investigators and can be found in the BMS-936558 (nivolumab) Investigator Brochure:

- Suspected Pulmonary Toxicity
- Diarrhea and Colitis
- Suspected Hepatotoxicity (including asymptomatic LFT elevations)
- Suspected Endocrinopathy
- Suspected Nephrotoxicity

In addition, the ipilimumab Investigator Brochure⁵ includes Management Algorithms for the following adverse reactions:

- GI Toxicity
- Hepatotoxicity
- Skin Toxicity
- Endocrinopathy
- Neurological Toxicity
- Other immune-mediated adverse reactions, including ocular manifestations

It should be noted that beginning with the first dose of Induction Period 2, adverse events may be related to the drug given in Induction Period 2, the prior drug given in Induction Period 1, or to both drugs. Therefore, it is recommended that the Management Algorithms in both the BMS-936558 (nivolumuab) Investigator Brochure and the ipilimumab Investigator Brochure be consulted for assistance with managing adverse events after the beginning of Induction Period 2.

4.3.4.1 Dose Omissions for Nivolumab or Ipilimumab

Doses of nivolumab or ipilimumab should be omitted (not delayed) if any of the following criteria are met:

- Any Grade 2 non-skin, drug-related adverse event, with the following exceptions:
 - Grade 2 drug-related fatigue or laboratory abnormalities do not require dose omission
- Any Grade 3 skin, drug-related adverse event
- Any Grade 3 drug-related laboratory abnormality, with the following exceptions for lymphopenia, leukopenia, AST, ALT, or total bilirubin:
 - Grade 3 lymphopenia or leukopenia does not require dose omission
 - If a subject has baseline AST, ALT, or total bilirubin that is within normal limits, omit dosing for drug-related Grade ≥ 2 toxicity
 - If a subject has baseline AST, ALT, or total bilirubin within the Grade 1 toxicity range, omit dosing for drug-related Grade ≥ 3 toxicity
- Any adverse event, laboratory abnormality, or intercurrent illness which, in the judgment of the investigator, warrants omitting the dose of study medication

If the criteria to resume treatment (specified in Section 4.3.4.3) are met within the dosing window (Week $X \pm 3$ days), then the dose may be given.

4.3.4.2 Criteria to Resume Treatment with Nivolumab or Ipilimumab

Subjects may resume treatment with nivolumab or ipilimumab when the drug-related AE(s) resolve to Grade ≤ 1 or baseline value, with the following exceptions:

• Subjects may resume treatment in the presence of Grade 2 fatigue

• Subjects who have not experienced a Grade 3 drug-related skin AE may resume treatment in the presence of Grade 2 skin toxicity

- Subjects with baseline AST/ALT or total bilirubin in the Grade 1 toxicity range who require dose omissions for reasons other than a 2-grade shift in AST/ALT or total bilirubin may resume treatment in the presence of Grade 2 AST/ALT or total bilirubin
- Drug-related pulmonary toxicity, diarrhea, or colitis must have resolved to baseline before treatment is resumed
- Drug-related endocrinopathies adequately controlled with only physiologic hormone replacement may resume treatment

If dosing is interrupted > 6 weeks, the subject must be permanently discontinued from study treatment with that particular drug, except as specified in Section 4.3.6.2.

4.3.4.3 Treatment of Infusion Reactions Related to Nivolumab or Ipilimumab

Infusion reactions related to nivolumab or ipilimumab may occasionally occur, manifested by fever, chills, rigors, headache, rash, pruritus, arthalgias, hypotension, hypertension, bronchospasm, or other allergic-like reactions. All Grade 3 or 4 infusion reactions should be reported within 24 hours to the study medical monitor and reported as an SAE if it meets the criteria. Infusion reactions should be graded according to NCI CTCAE (Version 4.0) guidelines.

Treatment recommendations are provided below and may be modified based on local treatment standards and guidelines, as appropriate:

For Grade 1 symptoms: (Mild reaction; infusion interruption not indicated; intervention not indicated).

Remain at bedside and monitor subject until recovery from symptoms. The following prophylactic premedications are recommended for future infusions: diphenhydramine 50 mg (or equivalent) and/or acetaminophen/paracetamol 325 to 1000 mg at least 30 minutes before additional nivolumab or ipilimumab administrations.

For Grade 2 symptoms: (Moderate reaction requires therapy or infusion interruption but responds promptly to symptomatic treatment [eg, antihistamines, non-steroidal anti-inflammatory drugs, narcotics, corticosteroids, IV fluids]; prophylactic medications indicated for ≤ 24 hours).

Stop the nivolumab or ipilimumab infusion, begin an IV infusion of normal saline, and treat the subject with diphenhydramine 50 mg IV (or equivalent) and/or acetaminophen/paracetamol 325 to 1000 mg; remain at bedside and monitor subject until resolution of symptoms. Corticosteroid therapy may also be administered as appropriate. If the infusion is interrupted, then restart the infusion at 50% of the original infusion rate when symptoms resolve; if no further complications ensue after 30 minutes, the rate may be increased to 100% of the original infusion rate. Monitor subject closely. If symptoms recur, then no further nivolumab or ipilimumab will be administered at that visit.

For future infusions, the following prophylactic premedications are recommended: diphenhydramine 50 mg (or equivalent) and/or acetaminophen/paracetamol 325 to 1000 mg should be administered at least 30 minutes before nivolumab infusions. If necessary, corticosteroids (up to 25 mg of SoluCortef or equivalent) may be used.

For Grade 3 or 4 symptoms: (Severe reaction, Grade 3: prolonged [ie, not rapidly responsive to symptomatic medication and/or brief interruption of infusion]; recurrence of symptoms following initial improvement; hospitalization indicated for other clinical sequelae [eg, renal impairment, pulmonary infiltrates]. Grade 4: Life threatening; pressor or ventilatory support indicated).

Immediately discontinue infusion of nivolumab or ipilimumab. Begin an IV infusion of normal saline and treat the subject as follows: Recommend bronchodilators, epinephrine 0.2 to 1 mg of a 1:1000 solution for subcutaneous administration or 0.1 to 0.25 mg of a 1:10,000 solution injected slowly for IV administration, and/or diphenhydramine 50 mg IV with methylprednisolone 100 mg IV or equivalent), as needed. Subject should be monitored until the Investigator is comfortable that the symptoms will not recur. Nivolumab or ipilimumab will be permanently discontinued. Investigators should follow their institutional guidelines for the treatment of anaphylaxis. Remain at bedside and monitor subject until recovery of the symptoms.

In case of late-occurring hypersensitivity symptoms (eg, appearance of a localized or generalized pruritus within 1 week after treatment), symptomatic treatment may be given (eg, oral antihistamine or corticosteroids).

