4.3.6 Nivolumab and/or Ipilimumab Treatment Discontinuation Criteria

4.3.6.1 Permanent Discontinuation Criteria for Both Nivolumab and Ipilimumab

All further study treatment (both nivolumab and ipilimumab) must be permanently discontinued if any of the following occurs during treatment with either nivolumab or ipilimumab:

Any Grade 4 drug-related adverse event or laboratory abnormality, except for the following events which do not require discontinuation

- Grade 4 neutropenia \leq 7 days
- Grade 4 lymphopenia or leukopenia
- Isolated Grade 4 electrolyte imbalances/abnormalities that are not associated with clinical sequelae and are corrected with supplementation/appropriate management within 72 hours of their onset
- Any drug-related adverse event which requires treatment with any immunosuppressive therapy other than corticosteroids (eg, infliximab, mycophenylate)
- Any adverse event, laboratory abnormality, or intercurrent illness which, in the judgment of the Investigator, presents a substantial clinical risk to the subject with continued dosing of nivolumab or ipilimumab
- Clinical or radiographic progression associated with rapid clinical deterioration which, in the judgment of the Investigator, is unlikely to benefit from further study treatment (nivolumab or ipilimumab).

4.3.6.2 Permanent Discontinuation Criteria for One Study Treatment (Discontinuation of Nivolumab Only or Discontinuation of Ipilimumab Only)

If any of the following occurs during treatment with either nivolumab or ipilimumab, treatment with **that particular drug** must be permanently discontinued:

- Any Grade 2 drug-related uveitis or eye pain or blurred vision that does not respond to topical therapy and does not improve to Grade 1 severity within the re-treatment period OR requires systemic treatment
- Any Grade 3 non-skin, drug-related adverse event lasting > 7 days, with the following exceptions for laboratory abnormalities, drug-related uveitis, pneumonitis, bronchospasm, colitis, diarrhea, hypersensitivity reactions, and infusion reactions:
- Grade 3 drug-related uveitis, pneumonitis, bronchospasm, diarrhea, colitis, hypersensitivity reaction, or infusion reaction of any duration requires discontinuation
- Grade 3 drug-related laboratory abnormalities do not require treatment discontinuation except:
- Grade 3 drug-related thrombocytopenia > 7 days or associated with bleeding requires discontinuation

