8 STATISTICAL CONSIDERATIONS

8.1 Sample Size Determination

This trial is an estimation trial. Sample size in this study will be approximately 40 subjects per cohort and is not based on power considerations. Tables below provide the 95% confidence intervals computed from different observed rates. Those tables indicate what would be the reliability of the AE rate estimates for N=40 (Table 8.1-1) and N=35 (see Table 8.1-2) treated subjects. A threshold of 45% will be applied to the upper limit of the confidence interval as an informal guideline for high toxicity

Thirty-five subjects per cohort will be the minimum number of subjects receiving treatment in Induction Period 2. For that purpose, randomization will stay open until at least 40 subjects in each cohort have been treated with at least one dose of study treatment in Induction Period 1 and 35 subjects in each cohort have received at least one dose of study treatment in Induction Period 2. Assuming a drop-out rate during induction period 1 would be at most 12.5%, at least 35 subjects would be treated in induction period 2 if 40 subjects are to be randomized per cohort.

Table 8.1-1: Exact 95% CI width and upper bound for AE rates up to 40% when observed in 40 subjects

Nb Subj with Rel Gr3-5 A	Rate of Rel Gr3-5 AE	Exact 95% CI width	Upper limit Exact 95%CI
4	10%	21%	23.7%
8	20%	27%	35.6%
10	25%	29%	41.2%
11	27.5%	29%	43.9%
12	30%	30%	46.5%
13	32.5%	31%	49.1%
14	35%	31%	51.7%
16	40%	32%	57%

Table 8.1-2: Exact 95% CI width and upper bound for AE rates up to 40% when observed in 35 subjects.

Nb Subj with Rel Gr3-5 AE	Rate of Rel Gr3-5 AE	Exact 95% CI Width	Upper Limit Exact 95%CI
4	11.4%	23.5%	26.7%
7	20%	28.5%	36.9%
9	25.7%	30.8%	43.3%
10	28.6%	31.7%	46.3%
11	31.4%	32.4%	49.3%
14	40%	34%	57.9%

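### Section 4.3.4.3 gives an infusion reaction that recurs after restart two consequences: a stop for one visit under Grade 2, and permanent discontinuation under the Grade 3 definition

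*Protocol*

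**What the plan says.** Protocol Section 4.3.4.3 asks for infusion reactions to be graded by NCI CTCAE v4.0 and then gives management by grade, introduced as recommendations that may be adapted to local standards.

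- **Grade 2.** The infusion is stopped and symptoms are treated. Then: "If the infusion is interrupted, then restart the infusion at 50% of the original infusion rate when symptoms resolve". On a return of symptoms: "If symptoms recur, then no further nivolumab or ipilimumab will be administered at that visit". A following paragraph begins "For future infusions, the following prophylactic premedications are recommended".
- **Grade 3 or 4.** The printed description of Grade 3 includes "recurrence of symptoms following initial improvement". The consequence is "Nivolumab or ipilimumab will be permanently discontinued". Grade 3 or 4 reactions are also to be reported to the study medical monitor within 24 hours.

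Section 4.3.6.2, which lists when one of the two drugs must be stopped for good, says of Grade 3 events: "hypersensitivity reaction, or infusion reaction of any duration requires discontinuation". It also bars nivolumab in the Continuation Period for subjects who permanently discontinued it during induction.

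Section 8.3.1 defines the primary endpoint as the proportion of treated subjects with at least one treatment-related Grade 3-5 adverse event of any preferred term, graded by CTCAE v4.0, with onset in the induction window. Section 8.1 adds: "A threshold of 45% will be applied to the upper limit of the confidence interval as an informal guideline for high toxicity".

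**The concern.** A subject whose symptoms resolve during an interruption and come back on restart is described by the Grade 2 text and also has a feature that the Grade 3 text uses to define that grade. The Grade 2 text limits the stop to the current visit and moves on to later infusions. The Grade 3 text and Section 4.3.6.2 allow no later infusion of that drug. No sentence sends a recurrence from the Grade 2 text to the Grade 3 rule, and nothing distinguishes recurrence on restart from the recurrence meant under Grade 3.

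Three things are at stake for the subject: whether the drug is given again, whether the event goes to the medical monitor within 24 hours, and, if the drug was nivolumab, whether it can be given in the Continuation Period. A lesser matter is the grade recorded, because the line between Grade 2 and Grade 3 is also the counting line of the primary endpoint.

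**Working it through.** **Step 1: the same course under each text.** The course is: reaction, infusion stopped, symptoms resolve, restart at 50% of the rate, symptoms return.

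| Question | Grade 2 text, 4.3.4.3 | Grade 3 text, 4.3.4.3, with 4.3.6.2 |
|---|---|---|
| Does the course fit? | Yes, it is described step by step | Yes, recurrence after improvement is listed |
| Stop | That visit only | Permanent for that drug |
| Later infusions of that drug | Foreseen, with premedication | None |
| Report to medical monitor within 24 hours | Not required by this section | Required |
| Nivolumab in Continuation, if nivolumab was the drug | Not barred by this event | Barred |
| Counts towards primary endpoint | No, if recorded as Grade 2 | Yes, if related and in the induction window |

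The last four consequences all follow from the grade assigned or the paragraph followed.

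**Step 2: what the grading rule settles.** Sections 4.3.4.3 and 8.3.1 both name CTCAE v4.0. The only grade that the protocol prints against recurrence after improvement is Grade 3. Graded by that printed definition, the event is Grade 3 and counts. The endpoint rule is therefore fixed, and what remains is the risk that a site following the Grade 2 text records Grade 2.

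**Step 3: the plan's own figures.** The exact (Clopper-Pearson) 95% upper limit for x events in n subjects is the 0.975 quantile of a Beta(x+1, n−x) distribution. It reproduces Tables 8.1-1 and 8.1-2 near the 45% guideline:

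- 11/40: 43.9%; 12/40: 46.5%.
- 9/35: 43.3%; 10/35: 46.3%.

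**Step 4: size of one misgraded subject.**

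- Change in rate at N=40: 1/40 = 2.5 percentage points.
- Change in rate at N=35: 1/35 = 2.9 points. In Section 8.4.2 the subjects dosed in Induction Period 2, for whom 35 is the minimum, are the sensitivity set and not the primary one.
- One subject moves the upper limit across 45% only from exactly 11 to 12 of 40, or from exactly 9 to 10 of 35.

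For the subject's status to change, the event must be treatment-related, must have its onset in the induction window, and must be the subject's only related Grade 3-5 event.

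**Step 5: frequency.** The protocol gives none. Purely as an assumption, if 0% to 5% of subjects had such a recurrence, that would be 0 to 0.05 × 40 = 2 subjects per cohort. Not all of them would be misgraded or free of another qualifying event.

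**The case against.** The strongest reply is that the texts can be read in sequence. The Grade 2 heading describes the reaction at onset. The recurrence sentence assigns no grade and only says what to do at once. The premedication paragraph serves Grade 2 reactions generally, including those that never recur. The site would stop at that visit, grade the event by CTCAE v4.0, and apply the rule for that grade. The management text is modifiable advice, whereas Section 4.3.6.2 is mandatory and would prevail for a Grade 3 event.

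This does not remove the contradiction. The instruction limits the stop to one visit, the next paragraph speaks of later infusions, and no cross-reference tells the site that a recurrence changes the grade. A site that follows advice printed in the protocol can thereby break a mandatory rule in the same protocol.

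The reply does succeed on the endpoint. A reader might infer that the same event is inside or outside the primary endpoint depending on the paragraph used. The documents do not support that: grading is by CTCAE v4.0 in both places, no text ties the grade to the management paragraph, and the printed definition puts recurrence in Grade 3. That sites would record Grade 2 is a possibility, and nothing in the protocol shows that they do.

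**Conclusion.** The contradiction is real and stands in the current text. Its main effect is on conduct: re-dosing, 24-hour reporting and later nivolumab eligibility differ according to the paragraph a site follows.

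Misgrading in the primary numerator is a secondary risk and probably small. It is worth 2.5 points per affected subject at N=40, under the three conditions given in the working and at an unknown frequency. A reader might also infer that the toxicity conclusion is in jeopardy. That would need an exact boundary count, and the 45% threshold is an informal guideline in an estimation trial, so no such effect is shown.

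The conclusion assumes that the items in the printed Grade 3 description, which are separated by semicolons, are alternatives, so that recurrence alone is enough.

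**What to change.** Reconcile the Grade 2 and Grade 3 paragraphs of Section 4.3.4.3 with each other and with Section 4.3.6.2, so that recurrence after restart has one grade and one consequence. Which rule applies is for the sponsor's clinicians to decide. Query recorded Grade 2 infusion reactions in which the infusion was restarted and symptoms returned, and confirm their CTCAE v4.0 grade. Section 8.3.1 needs no change, because it already grades by CTCAE v4.0.

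The cost is a wording change and a targeted data query. The observed Grade 3-5 rate may rise slightly if some events are regraded.
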